- 7. Worker's compensation or personal injury related to lumbar spine (treatment outcomes may be affected by patient's personal interests [21]; could also run into potential issues with reimbursement).
- 8. Lactating women
- 9. Patients with end stage liver disease

During the preoperative office visit, the surgeon will inform patients that appear to meet study eligibility criteria, about the study, and discuss the differences between the three postoperative pain management alternatives, including their potential risks and benefits. The surgeon will make clear to the patient that consenting to be a part of the study means that the patient has agreed to be randomly assigned to one of the three postoperative pain management groups. The patient would be told that the random assignment is going to be determined by rolling a standard die. The patient would be informed that the patient's pain would be controlled regardless of group assignment and that no placebos would be used.

Patients who agree to learn more about the study will be approached by a designated and trained study physician assistant (PA), briefly informed about the study, and asked if they wish to complete the screening questionnaire (Appendix 1) to see if they may be eligible to participate. Once the screening questionnaire is completed by the patient, it will be reviewed by the PA to ask any required clarifying questions and obtain additional information to determine eligibility. Participants who appear to meet eligibility criteria will be reviewed by the PA with one of the study investigators prior to confirming if they are eligible to enroll in the study.

Patients who are deemed eligible to participate in the study and are willing to participate will be asked by the PA to complete the research informed consent. This document will be summarized verbally by the PA and potential participants will be given the opportunity to ask questions about the protocol or their involvement prior to providing consent. Those who agree to participate and provide research informed consent will be enrolled in the study, and given a copy of the research informed consent document. The patient's informed consent would be added to the patient's chart.

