On the day of surgery, in the operating room, the circulating nurse will roll a die to randomly assign the patient to one of the three pain management groups. The study intervention group (die roll outcome 1 or 2) will receive a local infiltration of EXPAREL and bupivacaine 0.5% w/v solution into the surgical site (1 level patients – 20 mL Exparel + 30 mL bupivacaine 0.5% w/v solution; 2 level patients – 20 mL Exparel diluted to 40mL + 30 mL bupivacaine 0.5% w/v solution). The two medications will not be combined in the same syringe to minimize the possibility of a direct interaction between the two. While to date, no such interaction has been confirmed, we will maintain a strict "no mixing of bupivacaine and Exparel in the same syringe" policy throughout this study. The second group (die roll outcome 3 or 4) will only be administered local infiltration of Exparel (1 level patients – 20 mL Exparel; 2 level patients – 20 mL Exparel diluted to 40 mL). The third group will be treated to a local infiltration of 30 mL bupivacaine 0.5% w/v solution. Anesthesiologists will use their usual pre-operative and intra-operative techniques for all study participants and both study groups will receive nurse-administered rescue opioids as needed.

The patients and all staff, including hospital nursing staff, case management, and physical therapists, will be blinded as to which pain management treatment the patient received. While the surgical team cannot be blinded because the appearance of the drugs is different, they will however, not be assessing the outcome measures.

The primary outcome in this study will be the mean postoperative pain score derived from the pain scores recorded by the nursing staff in each participant's clinical records using the visual analog scale of 0-no pain to 10-extreme pain, several times in each 24-hour period, for the entire duration of the patient's hospital stay. Adopting [20] assumptions of a target reduction in mean overall postoperative pain scores of 1 point on the VAS and our anticipated variance of 2, it is estimated using one-way analysis of variance that for a statistical power of 80% and significance level of 0.05, a minimum of 40 participants will be required in each study group for a total of 120 study participants. To minimize the possibility of dropouts or incomplete data impacting the analysis, a minimum of 45 participants will be enrolled in each study group, for a total of 135 enrollees.

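### Allocation by an operating-room die roll has no described record or check, so an altered allocation could go unrecorded and modest steering would be hard to detect.

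*Combined protocol and SAP*

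**What the plan says.** Study Methodology gives the whole allocation procedure: in the operating room on the day of surgery, "the circulating nurse will roll a die to randomly assign the patient". Two faces lead to each arm: "The study intervention group (die roll outcome 1 or 2) will receive a local infiltration of EXPAREL and bupivacaine", and "The second group (die roll outcome 3 or 4) will only be administered local infiltration of Exparel". The third group, by implication faces 5 and 6, has bupivacaine alone. In the consent discussion patients are told that "the random assignment is going to be determined by rolling a standard die".

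On blinding, the same section says that "the surgical team cannot be blinded because the appearance of the drugs is different", and adds that "they will however, not be assessing the outcome measures".

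The description ends at the roll. No list, concealment device, witness, log, rule on repeat rolls or check of the allocation against the drug given appears in the document. Protection of Human Subjects limits database access to the principal investigators, described as the spine surgeons and physician assistants. No independent holder of the allocation is named.

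Eligibility review, consent and enrolment are all described before the day-of-surgery roll.

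**The concern.** The causal comparison needs allocation to be independent of prognosis. Here the assignment comes into being as a die result in a room where the patient and the procedure are known. As the plan is written, nothing fixes the result at that moment, and there is no list against which the final allocations can be checked. If some rolls were set aside for patients expected to have a hard recovery, prognosis would differ between arms. The planned analysis of variance of mean pain would read that difference as a drug effect, or would mask a real one.

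Two features of the plan make this more than theoretical. The hypothesis favours the combination arm, so people in the room may have a preference. The target is at least 45 per arm within a total of 135, which can be met only by exactly 45/45/45. A die rarely delivers that, so there is an innocent motive to override a roll.

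**Working it through.** **Plan's own figure.** One-way ANOVA with three arms, alpha 0.05, variance 2 and means 0, 0.5 and 1 has noncentrality 40 × 0.5 / 2 = 10 at 40 per arm. Power is 0.805, so the stated 40 per arm reproduces. Sample size is not in question.

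**Inputs from the plan.** Three arms at 1/3 each, 135 enrolled, variance 2, target difference 1 point.

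**Assumed inputs, not in the documents.** Half the patients are foreseeably worse by 1.5 points. In a proportion r of those who roll bupivacaine alone, the die is rolled once more and the second result stands. All other patients are allocated fairly.

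**Formulae.** B is bupivacaine alone and C is the combination.

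- P(B | high pain) = (1 − r)/3 + r/9
- P(C | high pain) = 1/3 + r/9
- High-pain share of an arm = P(arm | high) / [P(arm | high) + 1/3]
- Bias = 1.5 × (share in C − share in B)
- Expected B count = 135 × ½ × [P(B | high) + 1/3]
- SD of a fair arm count = √(135 × 1/3 × 2/3) = 5.48

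| r | High-pain share, B | High-pain share, C | Bias (points) | Expected B count | SDs below 45 |
|---|---|---|---|---|---|
| 20% | 0.464 | 0.516 | 0.078 | 42.0 | 0.55 |
| 50% | 0.400 | 0.538 | 0.208 | 37.5 | 1.37 |
| 100% | 0.250 | 0.571 | 0.482 | 30.0 | 2.74 |

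In this direction of steering the bias works against the combination. Opposite steering reverses the sign.

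**Would the counts show it?** Take a 5% chi-square test of equal arm counts on 2 df, with noncentrality 135 × Σ(p − 1/3)²/(1/3). This is 0.30, 1.875 and 7.5 for the three rates, and power is 7%, 21% and 69%. Steering that left the arm totals unchanged would be invisible to this test.

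**Effect on error rates.** The standard error of a pairwise difference at 45 per arm is √(2 × 2/45) = 0.298. The biases are 0.26, 0.70 and 1.62 standard errors. With no true difference, P(|Z + shift| > 1.96) is about 5.8%, 11% and 37% instead of 5%. The last figure ignores the shrinkage of the B arm and is somewhat high.

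**Sensitivity.** Bias is proportional to the assumed gap. With a 1-point gap it is 0.05, 0.14 and 0.32 points. The 1.5-point gap uses 0.5 × 0.5 × 1.5² = 0.5625 of the planned variance of 2 (28%). That is compatible with the plan but generous for something foreseeable in the operating room.

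**Pressure from the target.** The chance that 135 fair rolls give exactly 45/45/45 is 135!/(45!³ × 3¹³⁵) = 0.6%.

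**The case against.** A reader might infer that selection bias here can be neither prevented nor detected. The documents do not support that. A fair die cannot be foreseen and is rolled after eligibility review, consent and enrolment, so the usual route, deciding whom to enrol from knowledge of the next assignment, is closed. Detection is weak rather than impossible: at a 100% re-roll rate the bupivacaine-alone arm would be expected to hold 30 patients, and that would be noticed. A baseline comparison might also reveal prognostic steering, although none is planned.

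A reader might also infer that the unblinded surgical team watches the roll, or that no record of it is kept. The first is a fair guess from the location but is not stated. The second turns silence into proof. The plan describes no record, which is different from showing that none exists. Nor does anything show that rolls would be altered.

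The sizes rest on assumed inputs, and the best-hidden case is also the least harmful: 0.08 points hardly moves the error rate. That stands. The middle case is the one that matters: about a fifth of the target effect, roughly double the nominal error rate, and usually missed by arm counts.

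Finally, the plan does intend logistic regression to examine confounding. It names no covariates, it does not suit a mean pain score, and it could adjust only for prognosis that had been recorded. It does not close the gap.

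**Conclusion.** The concern holds in a limited form. The randomisation is genuine in principle, but as described it cannot be audited. The exposure is alteration at or after the roll, or loss of a patient once the arm is known; it is not foreknowledge at enrolment. The illustrative bias runs from about 0.08 to 0.48 points against a 1-point target. It depends on the assumed half share of high-pain patients, the 1.5-point gap, the re-roll rates and steering in one direction. Up to a 50% re-roll rate, arm counts would probably not reveal it. This should be changed, because the trial could not otherwise show that its allocations stood as rolled and the remedy is inexpensive.

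**What to change.** In both places in Study Methodology where the die appears (consent discussion and day of surgery), replace it with a computer-generated list. Someone outside the operating team, for example the research office or pharmacy, prepares and holds the list. Assignments are issued in sequentially numbered, opaque, sealed envelopes. Once eligibility is confirmed, the circulating nurse opens the next envelope, signs and times it, and retains it. At the end, the list, the envelopes and the drug given are reconciled. State that every randomised patient is analysed as allocated, which covers patients dropped after the result is known.

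The list must keep the die's one real strength, its unpredictability. If it is blocked to reach 45 per arm, block sizes should vary and be unknown to the operating team, who see each treatment given.

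The cost is about 135 envelopes, a short amendment, one changed sentence in the consent discussion, and a small preparation and reconciliation task. No extra patients are needed and the sample size is unchanged. Envelopes held on site reduce tampering but do not eliminate it, so the reconciliation step should not be dropped.

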Although short-term opioids can be effective to manage moderate to severe pain, they are associated with a variety of opioid related adverse events (ORAEs), including potentially incapacitating side effects and serious adverse events. For postsurgical pain, patients are at greatest risk for ORAEs during the first 24 hours after surgery when their opioid use is highest [11]. The use of opioids to manage postsurgical pain may be of particular concern for spine surgery, since many patients are already using opioids prior to their surgical procedure. This increases the possibility of ORAEs with higher perioperative doses and continued use beyond the perioperative period [3]. In addition, consumption of opioids is often an outcome measure in spine surgery, and continued or increased use is considered an indicator that the surgical procedure was not successful [12]. It may therefore be beneficial to minimize the amount of opioids consumed for postsurgical pain.

Given the limitations of current approaches to managing postsurgical pain, as well as the consequences of not adequately managing pain following surgical procedures, researchers are continually developing and investigating new approaches that provide optimal pain management. Postsurgical pain management regimens are also being evaluated and refined as a component of broader enhanced recovery after surgery (ERAS) initiatives intended to improve outcomes, reduce hospital LOS, and promote return to normal activities following elective surgical procedures [13]. These initiatives generally favor approaches to manage postsurgical pain that may increase early ambulation and discharge (e.g. regional or local analgesia with local anesthetics) while discouraging those that may decrease them (e.g. IV PCA with opioids).

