- 5. Reduced time to achieve physical therapy discharge criteria (criteria set according to each patient's living situation, preoperative physical function, comorbidities, and other goals)
- 6. Reduced inpatient length of stay (LOS)

Study Benefits to Virtua

This study could potentially benefit Virtua in several ways. If Exparel is shown to reduce postoperative pain for spine surgery patients, and consequently reduce their opioid consumption for postoperative pain management, then there could be the potential to see an improvement in patient satisfaction with regards to pain management. In addition, Virtua could stand to gain some cost savings if Exparel is shown to support decreased incidence of ORAEs such as respiratory depression, leading to reduced time to physical therapy discharge criteria and consequently reduced LOS.

If on the other hand, the study indicates that the more expensive Exparel is no more effective at managing postoperative pain compared to the cheaper alternatives, then Virtua stands to directly gain significant cost savings by adopting the use of the cheaper options as standard practice.

Study Methodology

Patients who meet all of the following inclusion criteria may be eligible to participate in the study if:

- 1. Age 18 or older;
- 2. Primary indication is low back pain, lumbosacral radiculopathy, lumbar disc degeneration, lumbar disc herniation, stenosis, spondylolisthesis, spondylolysis, or deformity requiring surgical intervention;
- 3. Scheduled to undergo primary, 1 or 2 level, posterior lumbar laminectomy with or without fusion, discectomy with fusion, or fusion at Virtua Memorial Hospital;
- 4. Willing to provide informed consent, participate in study, and comply with study protocol.

Patients who meet any of the following criteria may not be eligible to participate:

- 1. Hypersensitivity or allergy to local anesthetics;
- 2. Pregnant or contemplating pregnancy prior to surgery;
- 3. Previous surgery in lumbar spine (i.e. other than microdiscectomy);
- 4. Prior treatment for alcohol, recreational drug, or opioid abuse;
- 5. Serious spinal conditions (e.g. spinal cord compression, cauda equina syndrome, spinal infection, spinal tumor, spinal fracture, inflammatory or systemic spinal arthritis);
- 6. Surgery involving more than 2 vertebral levels;

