Secondary outcome measures in this study include total opioid consumption. All opioid analgesics used in the hospital will be recorded in the participant's clinical record, including: Name of medication (e.g. morphine); Dose administered (e.g. 10mg); Route of administration (e.g. IV, IM, oral); Reason for administration (e.g. surgical site pain). All opioid analgesics will be converted into oral mg morphine equivalent to determine the total dose of opioids used during the hospital stay using the conversion factors in Appendix 2. Other secondary outcome measures include mean time to achieve physical therapy discharge criteria, mean LOS, and incidence of ORAEs. ORAEs will be documented using the checklist shown in Appendix 3 with assistance from a nurse during every nursing shift (i.e. every 12 hours) until hospital discharge).

Means will be compared among all the three arms using analysis of variance, proportions will be compared using chi-square tests, and logistic regression will be used to analyze for confounding effects. All statistical analyses will be conducted in Minitab 16 Statistical Software.

Protection of Human Subjects

Throughout the study, the principal investigators (Virtua Memorial spine surgeons and PAs), will be the only ones with access to the data collection database. Following the completion of the study, all personal health information collected, including name, gender, age, significant medical comorbidities, and postoperative complications, will be de-identified as soon as possible prior to data analysis and any subsequent publications or research submissions. Patient would be told participation is purely voluntary with no monetary reimbursement and minimal risk of being assigned to one of the three pain management groups.

References

- 1. Centers for Disease Control and Prevention (CDC). National Hospital Discharge Survey: 2006 Annual Summary. Vital and Health Statistics, 2010;13(168).
- 2. Centers for Disease Control and Prevention (CDC), Health, United States, 2012: With Special Features on Emergency Care. 2012: Hyattsville, MD.

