APPENDIX 3. INCIDENCE OF OPIOID RELATED ADVERSE EVENTS

Instructions

Please indicate if you have experienced any of the following symptoms in the past 12 hours:

Symptom	Yes	No	Comments
Constipation			
Falling			
Нурохіа			
Lethargy			
Nausea			
Postoperative ileus			
Respiratory depression			
Sedation			
Somnolence			
Unsteadiness			
Urinary retention			
Vomiting

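### The unblinded surgical team is barred only from assessing outcomes; if it also writes orders or decides discharge (not stated), length of stay, opioid total and analgesic cost are open to arm-aware decisions

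*Combined protocol and SAP*

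**What the plan says.** All the blinding provisions are in Study Methodology. Patients and staff, "including hospital nursing staff, case management, and physical therapists, will be blinded" to the treatment given. The surgical team is then excepted: "While the surgical team cannot be blinded because the appearance of the drugs is different, they will however, not be assessing the outcome measures". No other restriction on that team is stated.

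For postoperative analgesia, the plan says that "both study groups will receive nurse-administered rescue opioids as needed". It names who gives the rescue doses but not who prescribes them. Anesthesiologists keep their usual technique before and during surgery; postoperative orders are not mentioned.

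The affected outcomes appear in two places. The hypotheses include lower opioid consumption (2), lower cost of pain medication (3), shorter time to physical therapy discharge criteria (5) and "Reduced inpatient length of stay (LOS") (6). Study Methodology lists opioid consumption, time to criteria, LOS and opioid-related adverse events (ORAEs) as secondary outcomes; cost is not repeated there. The therapy criteria are individual to each patient. The plan does not say who sets or judges them, and no rule ties meeting them to leaving hospital.

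Protection of Human Subjects identifies "the principal investigators (Virtua Memorial spine surgeons and PAs") as the only people with database access during the study.

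**The concern.** Keeping a person from assessing outcomes works where the outcome is a judgement or a recorded score, such as pain or the ORAE checklist. It does nothing where the outcome is the result of a decision. LOS ends when someone discharges the patient. The opioid total and the cost of pain medication depend partly on what has been ordered, in what form and up to what ceiling.

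The team that knows the arm includes surgeons, and spine surgeons and PAs are the study's principal investigators. If these clinicians also write the orders or decide discharge, what they expect of a treatment can enter the outcome without anyone rating anything. A surgeon who trusts the combination might order less rescue opioid or discharge sooner. A surgeon wary of giving both drugs might observe those patients longer.

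At stake is the economic reading of the trial. Study Benefits to Virtua foresees fewer ORAEs "leading to reduced time to physical therapy discharge criteria and consequently reduced LOS", so LOS is the end of the proposed savings pathway.

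**Working it through.** The plan gives no figure for this point, so the check is mainly a comparison of texts. One calculation shows what the proposed descriptive check can and cannot do.

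**1. Which outcomes the stated safeguard covers**

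- *Pain score (primary):* recorded by blinded nurses, so the rating is protected. The mean is taken over the whole stay, so a changed discharge time changes the averaging window. The Background says pain eases over a few days; leaving earlier would drop late, lower readings and raise that patient's mean. Arm-aware opioid orders could also influence pain. Both routes are indirect.
- *ORAEs:* a patient checklist completed with a nurse's help each shift. The rating is protected; any effect would come through opioid dose or length of observation. The Background states that "patients are at greatest risk for ORAEs during the first 24 hours after surgery when their opioid use is highest", so a shorter stay would remove the lower-risk hours.
- *Time to therapy criteria:* therapists are blinded, but the plan does not say that they set and judge the criteria.
- *Opioid total and analgesic cost:* blinded nurses give rescue as needed, which limits the exposure. The prescriber is not stated, so the form and ceiling of orders are not covered.
- *LOS:* fixed by a discharge decision. Case management and therapists are blinded, which limits the exposure. The person who decides is not stated.

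**2. Whether the size can be computed**

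A bias in mean LOS would need the fraction of patients discharged early or late because of the arm, the time shifted, and the LOS SD. The documents give none of these. The order pathway would need the prescriber's role and the spread of opioid use, which are also absent. No size is therefore reported.

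**3. What the interval check can show**

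Inputs: 40 per arm and alpha 0.05 (Study Methodology). The plan's 40 reproduces for its primary outcome: three arms, variance 2, means 0, 0.5 and 1. The noncentrality is 40 × (0.25 + 0 + 0.25) / 2 = 10, and the F test with 2 and 117 df has power 0.805.

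For the interval from criteria met to discharge, the 95% CI half-width for an unadjusted pairwise difference is

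t(0.975, 78) × √(2/40) = 0.445 SD of the interval (0.419 with 45 per arm).

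To express this in LOS SDs, *assume* that time to criteria and LOS have equal SDs and correlation r. Then interval SD = LOS SD × √(2(1 − r)). At 40 per arm:

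| r (assumed) | interval SD / LOS SD | half-width in LOS SD |
|---|---|---|
| 0.5 | 1.000 | 0.445 |
| 0.8 | 0.632 | 0.282 |
| 0.9 | 0.447 | 0.199 |

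Across this range the check resolves differences no finer than about 0.20 to 0.45 LOS SD. It can expose a large shift but cannot exclude a small one.

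**The case against.** The strongest reply is that the harm rests on an unstated fact. The documents never say that surgeons discharge patients or write orders. The plan openly discloses that surgeons cannot be blinded and why, and it blinds everyone else who has daily contact with the patient. This stands, and it is why the point is conditional. If blinded clinicians already make these decisions, most of the concern falls away.

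Several stronger readings are tempting, and the documents do not support them:

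- *That the bias would favor the combination.* The hypotheses point that way, but Study Benefits to Virtua describes an institutional gain if Exparel proves no better, as well as if it works. Either direction is possible.
- *That LOS is the outcome chiefly at risk.* Arm-aware orders would act on opioid use and medication cost more directly than on LOS, and nothing in the documents measures that pathway. No ranking is justified.
- *That a false-positive rate for the LOS comparison can be quoted.* Any such rate depends on an invented early-discharge fraction and LOS SD. Different choices move it from close to the nominal 5% to several times that.
- *That arm-aware discharge would be invisible.* Time to criteria and LOS are both already compared across arms, so a marked discrepancy would show. What is missing is the within-patient interval with its CI and the count discharged before meeting criteria.
- *That exclusive database access means surgeons and PAs assess outcomes.* The plan says the surgical team will not.

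It is also fair to say that the interval check is limited. It cannot separate bias from a real drug effect: "Postoperative ileus", urinary retention or vomiting, all on the Appendix 3 checklist, could delay discharge after the therapy criteria are met, and one treatment may cause less of them.

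**Conclusion.** The concern holds conditionally. Barring the unblinded team from outcome assessment leaves orders and discharge uncovered, and the plan does not say who is responsible for either. If the surgical team is, LOS, the opioid total and analgesic cost are open to arm-aware decisions in either direction. Blinded nurses, therapists and case management reduce the exposure without closing it.

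The size is unknown and cannot be derived from the documents. Severity is low to moderate: these outcomes are not primary, the primary score is recorded by blinded staff, and an unblinded surgeon is hard to avoid with drugs that look different. It is still worth acting on, because the remedy costs little and these outcomes carry the trial's economic argument.

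**What to change.** State who writes postoperative orders and who decides discharge; if both are blinded, little more is needed. Otherwise:

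1. **Orders.** Enter postoperative analgesic orders from one order set common to all three arms before the die is rolled, and log later changes with a reason. Clinicians decide the content, and no change a patient needs is delayed.
2. **Criteria.** State that the blinded physical therapist sets and judges each patient's discharge criteria.
3. **Reporting.** Beside LOS, report by arm the interval from criteria met to discharge, with a 95% CI for the differences, and the number discharged before meeting criteria. Treat both as descriptive, with no pass rule. If LOS differs while time to criteria does not, interpret LOS cautiously and look at the ORAEs that could delay discharge.

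Cost: protocol wording, earlier order entry, and a logged reason for each order change. Time to criteria and LOS are already planned, so the interval needs no new measurement if both are kept as date and time. No extra staff are needed and the sample size does not change. The other downside is a more cautious claim about LOS.

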Approved by the FDA in 2011, Exparel (liposomal bupivacaine) is a sustained-release version of the local anesthetic bupivacaine. While bupivacaine may last 6 to 12 hours to provide post-surgical relief, it is claimed that Exparel can last up to 72 hours after local infiltration at the surgical site [14]. Different studies have also compared the efficacy of Exparel to bupivacaine for the management of postsurgical pain following various surgical procedures, including inguinal hernia repair, breast augmentation, and TKA [15-20]. While some of these studies have supported the efficacy of Exparel to provide superior relief of postsurgical pain, others have found bupivacaine to be just as effective [20]. There is still however, a paucity of literature on the efficacy of Exparel for spine surgery pain management.

Study Questions/Objectives and Hypothesis

This study is aimed at prospectively examining clinical and economic outcomes when managing postsurgical pain using local infiltration of Exparel for patients undergoing primary, 1 or 2 level, lumbar laminectomy with or without fusion. There is a growing body of evidence suggesting that combining Exparel with a short acting numbing medicine gives much better pain coverage. The rationale is that Exparel can take several hours to have anesthetic onset and conventional thinking believes that if we can cover the immediate postoperative pain better with an immediate acting anesthetic to bridge the onset gap, then better outcomes will be achieved. The combination of these medications have been used in various studies previously in other areas of the body both in orthopedics and non-orthopedics and no adverse effects of combining these medications and in similar quantities/dosing have been observed [22,23,24]. To this end, we hypothesize that compared to patients that only received local infiltration of bupivacaine or only administered Exparel, the intervention group treated to a combination of Exparel and bupivacaine would, during their hospital stay following surgery, experience:

- 1. Reduced mean postoperative pain score (Wong-Baker pain faces scale of 0-no pain, to 10-extreme pain)
- 2. Reduced total consumption of opioids (in mean morphine equivalents)
- 3. Reduced overall cost of postoperative pain control medications
- 4. Decreased incidence of ORAEs

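### Time to physical therapy discharge criteria is a time-to-event outcome seen only in hospital, but it is compared as a mean by ANOVA, with no place for patients who leave without meeting the criteria.

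*Combined protocol and SAP*

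**What the plan says.** Hypothesis 5, under Study Questions/Objectives and Hypothesis, is "Reduced time to achieve physical therapy discharge criteria". The criteria are individual to the patient: "criteria set according to each patient's living situation, preoperative physical function, comorbidities, and other goals". All six hypotheses concern what patients "would, during their hospital stay following surgery, experience", so observation stops when the patient leaves.

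Under Study Methodology the outcome becomes a mean: "Other secondary outcome measures include mean time to achieve physical therapy discharge criteria, mean LOS, and incidence of ORAEs". The analysis is "Means will be compared among all the three arms using analysis of variance, proportions will be compared using chi-square tests", and logistic regression is named only for confounding. No censoring rule or time-to-event method appears, and nothing says what value is given to a patient who leaves before meeting the criteria.

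The only provision for incomplete data is extra enrolment: "To minimize the possibility of dropouts or incomplete data impacting the analysis, a minimum of 45 participants will be enrolled in each study group".

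**The concern.** ANOVA needs one completed time per patient. That is no obstacle for length of stay, which every discharged patient has. It is an obstacle for time to the therapy criteria, because a patient who is transferred, withdraws or is discharged without meeting them has no such time.

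Two makeshift routes are open to the analyst. One omits the patient. The other enters the discharge time as if the criteria had been met. The first treats a possibly poor recovery as absent, and the second treats it as a success. Enrolling 45 instead of 40 per arm restores numbers but cannot correct loss that depends on the outcome.

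The section on benefits to the hospital makes this outcome the link from fewer opioid-related events to shorter stay and cost savings. A biased comparison would therefore feed the adoption decision, although the primary pain analysis would not change.

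**Working it through.** **1. The plan's own figure.** The only sizing is for the pain score: "a target reduction in mean overall postoperative pain scores of 1 point on the VAS", variance 2, power 80%, alpha 0.05. With three means at -0.5, 0 and 0.5, the noncentrality is n × Σ(μᵢ − μ̄)²/σ² = 40 × 0.5/2 = 10, and power is 80.5%. The stated 40 per arm is reproduced. Enrolling 45 allows a loss of 1 − 40/45 = 11.1%. Neither figure concerns the therapy outcome, for which the documents give no mean, SD or non-attainment rate. What follows is illustration on assumed inputs.

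**2. Assumed model.** Take the combination arm against one comparator, with lognormal times, medians m of 32 h and 42 h, and log-SD s of 0.5 or 0.7. Patients not meeting the criteria by a common cut-off T leave without a value. With a = ln(T/m)/s:

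- full mean M = m × exp(s²/2)
- proportion not attaining = 1 − Φ(a)
- mean after dropping non-achievers = M × Φ(a − s)/Φ(a)
- mean with departure time entered = M × Φ(a − s) + T × (1 − Φ(a))

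Example with s = 0.5 and T = 60 h:

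- Slower arm: M = 42 × exp(0.125) = 47.59 h, a = 0.713, mean after dropping = 47.59 × 0.5845/0.762 = 36.5 h.
- Faster arm: M = 36.26 h, a = 1.257, mean after dropping = 36.26 × 0.7755/0.8957 = 31.4 h.
- The true difference is 47.59 − 36.26 = 11.3 h. The estimate is 36.5 − 31.4 = 5.1 h, or 45%.

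**3. Dropping non-achievers.**

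| Log-SD (true difference) | Cut-off (h) | Not attaining, slower arm | Share of true difference kept |
|---|---|---|---|
| 0.5 (11.3 h) | 60 / 72 / 96 | 24 / 14 / 5% | 45 / 58 / 77% |
| 0.5 | 120 / 144 / 168 | 1.8 / 0.7 / 0.3% | 88 / 94 / 97% |
| 0.7 (12.8 h) | 60 / 72 / 96 | 31 / 22 / 12% | 30 / 38 / 52% |
| 0.7 | 120 / 144 / 168 | 6.7 / 3.9 / 2.4% | 64 / 73 / 80% |

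**4. Entering the departure time instead.** At 60/72/96 h the estimated difference is 7.7/9.0/10.4 h of 11.3 h (log-SD 0.5), or 6.4/7.7/9.5 h of 12.8 h (log-SD 0.7). The shrinkage is milder but still present.

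**5. Other reasons for leaving.** A second assumed set uses medians 48 h and 40 h, log-SD 0.5, true difference 9.04 h, with patients lacking a value dropped:

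| Who has no value | Share of true difference kept |
|---|---|
| 5-11% of each arm, unrelated to time | 100% |
| Departures at random times, same in both arms | 88-97% |
| Slowest 2 / 5 / 10% of each arm | 96 / 92 / 87% |
| Common cut-off 72 / 96 / 120 / 144 h | 46 / 66 / 80 / 88% |
| Slowest 5 / 10%, slower arm only | 52 / 22% |
| Slowest 5 / 10%, combination arm only | 140 / 165% |

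The direction therefore depends on why patients leave.

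**6. Effect on the test.** In the step 2 model at log-SD 0.5 with a 60 h cut-off and 45 per arm, simulated power is about 43% for the mean comparison after dropping. It is about 69% for a rank-based test that keeps non-achievers as worst.

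**The case against.** The strongest reply is that few patients may lack a value. These are discharge criteria, tailored to the patient, and the benefits section says that reaching them sooner shortens the stay. On that reading they largely govern discharge. Eligibility is limited to primary one- or two-level surgery, with serious spinal conditions excluded. If everyone meets the criteria in hospital, comparing means is legitimate, and hours are a useful unit for cost and stay.

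Dropping slow patients also reduces variance, so the test suffers less than the estimate. With 45 per arm and log-SD 0.5, the expected difference over its standard error goes from 2.38 to 2.28 at 96 h and 2.36 at 120 h. At log-SD 0.7 it goes from 1.60 to 1.43 and 1.52. A marked fall (2.38 to 1.82) needs the 60 h cut-off and 24% non-attainment in the slower arm.

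Much of this stands. It limits the likely size, and it rules out a stronger reading that a reader might infer: that the plan discards the slowest patients and so understates the benefit of the combination. The documents never say that such patients are excluded. They give no rate, and they do not tie leaving early to slow recovery.

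The reply does not remove the gap. Nowhere is meeting the criteria made a condition of discharge, and therapy time and length of stay are listed as separate outcomes. The planned method has no valid place for a non-achiever, however few there are. Because the direction of bias cannot be predicted, the handling needs to be fixed in advance.

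**Conclusion.** The concern holds as a mismatch between outcome and method. Under the planned ANOVA, a patient who leaves without meeting the criteria can only be omitted or miscounted. If slow patients are lost in the same way in all arms, the difference is probably understated, but other patterns of loss give no bias or an exaggerated difference.

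No size can be stated for this trial. The 30-77% and 64-97% ranges rest on assumed lognormal times, medians and common departure cut-offs. The lower range needs about 5-31% non-attainment in the slower arm, and the upper range about 0.3-7%. The change is worth making before analysis. The consequence is confined to hypothesis 5 and what is inferred from it, and the primary analysis is unchanged.

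**What to change.** - **Data:** record for each patient whether and when the criteria were met, or the time and reason for leaving without meeting them.
- **Analysis:** for this outcome, replace ANOVA with Kaplan-Meier or cumulative incidence curves and a three-arm log-rank test.
- **Non-achievers:** keep patients discharged or transferred without meeting the criteria as not having met them, either censored beyond the longest observed time or treated as a competing event. They should be neither missing nor censored at discharge, because censoring there would be informative.
- **Reporting:** give the proportion meeting the criteria by arm. Mean times among those who met them may stay as a labelled descriptive summary.

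The cost is a small addition to data collection and a change of test for one secondary outcome. The main result becomes a curve or median rather than a difference in mean hours, which is less direct for costing. The software named in the plan should be checked for the chosen method. Sample size and the primary analysis need no change.
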